## 6. Trial endpoints

Clinical endpoints will be analyzed in all subjects who are enrolled, regardless of whether the trial treatment administered successfully completed for the desired duration. A subject will be considered enrolled in the trial when he/she is randomized to one of the treatment arms of the study. All endpoints are subject-based unless otherwise specified.

The primary endpoint is subject-based of the longer of a 12-month or end of study treatment endpoint of the first occurrence of index limb arterial occlusion, surgical intervention,

endovascular intervention, amputation of the affected limb (primary patency and limb salvage), MI, ischemic stroke or death (survival)

The secondary endpoints are subject-based on the longer of a 12-month or end of study treatment endpoints that include: (a) the first occurrence of any individual component of the primary endpoint, (b) the first occurrence of the following during follow-up: cardiovascular death, or MI, or ischemic stroke, or any amputation above the ankle and (c) severe bleeding defined according to the Global Utilization of Streptokinase and Tissue plasminogen activator for Occluded coronary arteries (GUSTO) classification

The tertiary endpoint is based on the longer of a12-month or end of study treatment moderate bleeding according to the GUSTO classification

Clinically indicated DAPT duration will be based on the longest pre-discharge following index peripheral intervention procedure DAPT duration. This will be determined based on: peripheral intervention device IFUs, preceding coronary intervention, acute coronary syndrome or other guideline-based clinical or device specific DAPT duration.

Study treatment will be discontinued at the first occurrence of a primary endpoint as defined in the table below. Patients, however, can resume taking aspirin, Clopidogrel, or both based on their provider's clinical decision.

Primary endpoint definition(s)	Secondary/Tertiary endpoint definition(s)
Occlusion of the target limb documented by any imaging procedure performed clinically	As described in section 6, except for:
any maging procedure performed ennearly	GUSTO bleeding criteria:
Any surgical or endovascular	1. Severe or Life-threatening: Intracerebral hemorrhage resulting in substantial
revascularization procedure on the index limb	hemodynamic compromise requiring treatment
Amputation above the ankle of the index	2. Moderate: Requiring blood transfusion but not resulting in hemodynamic

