## 14. Sample size estimate

The occurrence of the primary endpoint is expected to be approximately 49% in the control group, derived on the basis of current literature review and preliminary data form XLPAD registry.

A 30% relative risk reduction in the incidence of primary endpoint would be clinically important. To detect a 30% relative reduction in the primary event rate from 49% to34%  with 80% power at the two-sided, 0.05 significance level, assuming a 12-month recruitment period and a 10% dropout rate at 1 year, a total of 404 patients will be randomized (202in each group) and followed-up for endpoints for longer of a 12-month or end of study treatment period.

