## **19. Statistical analysis**

Continuous variables will be summarized as mean±standard deviation and compared using the t-test or the Wilcoxon rank-sum test, as appropriate. Discrete variables will be presented as frequencies and group percentages and compared using the chi-square test. For all comparisons a two-sided probability of <0.05 will be considered statistically significant. All analyses were performed using the SAS 9.4 or recent version (SAS Institute Inc., Cary, North Carolina). Primary endpoint will be assessed as per an intention-to treat principle.

Subsequent analysis will also be performed based on per-protocol basis. Pre-specified

subgroup analyses will include:

- 1. Stent vs. non-stent groups
- 2. DES vs. BMS
- 3. Above and below-the knee intervention

4. Claudication vs. CLI groups

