#### **Secondary Endpoints**

Secondary endpoints will be summarized at the specified time points using the descriptive statistics described above, individually or in comparison between the treatment groups. Statistical analyses of the following secondary endpoints will be summarized for descriptive purposes and without adjustments for multiplicity:

- Changes in ABI from baseline to hospital discharge, 30 days, 6 months and 12 months post-procedure will be analyzed using paired two-sided Student *t*-tests.
- Changes in Walking Impairment Questionnaire scores from baseline to 30 days, 6 month, and 12 months post-procedure will be analyzed using paired two-sided Student *t*-tests.
- Freedom from Target Lesion Revascularization Kaplan-Meier estimates and plots will be presented to 12 months post-procedure

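### The rule that any two-sided p<0.05 is significant covers every secondary, tertiary and subgroup comparison, with no multiplicity control, no interaction test and no clear line between descriptive and inferential analyses

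*Combined protocol and SAP*

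**What the plan says.** Section 19 (Statistical analysis), repeated in the Synopsis, gives the rule: "For all comparisons a two-sided probability of <0.05 will be considered statistically significant". It names the chi-square test for discrete variables. It then lists four subgroup analyses: stent or no stent, drug-eluting or bare-metal stent, claudication or critical limb ischemia (CLI), and "3. Above and below-the knee intervention". No test is named for any of them.

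Section 6 lists three kinds of secondary endpoint. The first is "a) the first occurrence of any individual component of the primary endpoint". The others are a cardiovascular composite and severe bleeding. Moderate bleeding is tertiary.

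Section 20 (Secondary Endpoints) opens by sending secondary endpoints to the descriptive statistics given earlier, and it allows comparison between groups. It then says: "Statistical analyses of the following secondary endpoints will be summarized for descriptive purposes and without adjustments for multiplicity". The list that follows is change in ABI, change in WIQ score, and freedom from TLR.

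The primary endpoint is handled separately. Section 17 names the intention-to-treat set for testing it and plans no interim efficacy analysis. Section 20 (Primary Endpoint) gives it a success rule based on 95% confidence bounds.

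**The concern.** Three sections disagree about which analyses are descriptive. The endpoints that Section 20 labels descriptive are not in the Section 6 list, and the endpoints that are in that list carry no such label. Read literally, Section 19 therefore attaches a significance verdict to every component, the cardiovascular composite, both bleeding endpoints and every subgroup comparison.

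Two things are at stake. First, an isolated p<0.05 among many comparisons could be reported as a finding with the protocol's backing. Second, if each subgroup stratum gets its own verdict, an effect that is the same in everyone will often look present in one stratum and absent in its partner. Comparing two verdicts does not test whether the effect differs.

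The knee split adds a practical difficulty. Section 10 admits subjects treated at more than one arterial level, so a subject treated both above and below the knee has no defined stratum.

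**Working it through.** **1. The plan's own figure.** The documents state no family-wise error rate. The only calculation with an error rate is the sample size in Section 14: "To detect a 30% relative reduction in the primary event rate from 49% to34"%, "with 80% power at the two-sided, 0.05 significance level, assuming a 12-month recruitment period and a 10% dropout rate at 1 year", giving 404.

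Per arm, n = [1.960·√(2·0.415·0.585) + 0.842·√(0.49·0.51 + 0.34·0.66)]² / 0.15² = 168.2. With continuity correction this is (168.2/4)·[1 + √(1 + 4/(168.2·0.15))]² = 181.3, so 182 per arm and 364 in total (stated: 368). Then 364/0.9 = 405 (stated: 404). The figure reproduces closely, and it concerns the primary endpoint only.

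**2. Counting comparisons.** Section 6 names seven components. Its definition table merges surgical and endovascular revascularization, which gives six. Adding the composite, severe bleeding and moderate bleeding makes ten or nine. Four subgroup factors with two levels each make eight strata.

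**3. Upper reference: independent tests, no true effect.** The chance of at least one p<0.05 is 1 − 0.95^k.

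| Family | k | Either direction |
|---|---|---|
| Secondary/tertiary, merged table | 9 | 37.0% |
| Secondary/tertiary, as listed | 10 | 40.1% |
| Subgroup strata | 8 | 33.7% |
| Nine endpoints plus strata | 17 | 58.2% |
| Ten endpoints plus strata | 18 | 60.3% |

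For results favouring the longer arm only, 1 − 0.975^18 = 36.6%.

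**4. Allowing for overlap.** The tests share subjects, so simulation is needed. The documents give no component rates, bleeding rates, correlations or subgroup shares; all are assumed. Four null scenarios were run, each with 8,000 trials of 368 subjects and chi-square tests. Component rates ranged from 1% to 40%, latent correlation from 0 to 0.7 and bleeding from 1% to 4%. Sixty percent of subjects were stented and the other splits were even.

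| At least one p<0.05, no true effect | Range |
|---|---|
| Ten endpoints, either direction | 34-38% |
| Eight strata, either direction | 26-27% |
| All 18, either direction | 49-52% |
| All 18, favouring the longer arm | 26-30% |
| Four interaction tests alone | about 20% |
| Ten endpoints plus four interaction tests | 48-50% |

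A separate model used 202 per arm and independent components at 14, 4, 27, 3, 3, 2 and 6% (composite about 48%), with bleeding at 1% and 3%. Shares were 60% stented, half of those drug-eluting, 30% below-knee and 35% CLI. It gave 51-52% for all 18 in either direction. Efficacy results favouring the longer arm, with bleeding excluded, occurred in 24-26%. Such results with a failed primary occurred in 22-23%.

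**5. Uniform true effect, strata read separately.** Take 49% versus 34% in everyone and an even split of 184 per arm, so 92 per arm in each stratum. The power within one stratum is Φ[(0.15 − 1.960·√(2·0.415·0.585/92)) / √(0.4743/92)] = Φ(0.106) = 54%. One pair then disagrees with probability 2·0.54·0.46 = 50%. Over four overlapping pairs with the shares in step 4, simulation gives 86-88% with at least one discordant pair.

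**6. Power of an interaction test.** With 184 per arm the standard error of the overall difference is √(0.4743/184) = 0.051. For an even split, the standard error of the difference between two stratum effects is twice that, 0.102. If the stratum effects differ by 15 percentage points, z = 0.15/0.102 = 1.48 and power is about 31%.

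**The case against.** The strongest reply is that the trial has one primary endpoint, one named analysis set, no interim efficacy look and a separate success rule for that endpoint in Section 20. All of that stands. The 0.05 sentence is therefore not the plan's only decision rule, and nothing here inflates the type I error of the primary test.

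The second reply is that Section 20 already treats secondary endpoints descriptively. Its opening sentence does point that way, but it also allows comparison between arms and refers back to Section 19, where the 0.05 rule stands. The explicit descriptive label covers only ABI, WIQ and TLR. The reply narrows the problem without removing it.

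Third, testing stratum by stratum is an inference, because no subgroup test is named. That is correct, and the strata figure and the 86-88% both depend on it. The overall null figure barely does: four interaction tests in place of eight strata still give 48-50%.

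Two stronger readings are tempting. A reader might infer that half of null trials would yield a positive claim for longer treatment. They would not: the 49-52% counts differences in both directions and includes bleeding, where significance would not be an efficacy claim. A reader might also infer that the plan lets a failed primary result be replaced by a secondary or subgroup finding. No section says so. That would be a misuse of the reporting rule, and in the model of step 4 it could arise in 22-23% of null trials.

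**Conclusion.** The point holds as a cheap improvement to the wording. The plan applies an unadjusted 0.05 rule to all comparisons, gives no interaction test, and is inconsistent between Sections 6, 19 and 20 on what is descriptive. The primary endpoint is not affected.

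With no true effect, about half of such trials (49-52%; 60% if the tests were independent) would show at least one nominally significant secondary, tertiary or subgroup difference in either direction. About a quarter (24-30%) would show one favouring the longer arm. The lower end of that range leaves out bleeding. With a uniform true effect, 86-88% would show a discordant subgroup pair.

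Confidence is high that control is missing. The percentages are less certain because they rest on assumed event rates, bleeding rates and subgroup shares, and on subgroups being tested stratum by stratum. They changed little across the scenarios tried. They use ten endpoints; with nine, the independent-test figure for all comparisons is 58% in place of 60%.

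**What to change.** In Section 19 and the Synopsis, replace the sentence on significance with wording to this effect:

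> The two-sided 0.05 significance level applies only to the intention-to-treat comparison of the primary endpoint. The secondary and tertiary endpoints in Section 6, the additional analyses in Section 20 and all subgroup analyses are exploratory. They are reported as between-arm estimates with 95% confidence intervals, without claims of statistical significance. Subgroup effects are assessed by a treatment-by-subgroup interaction test.

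Align Section 20 with this so that its descriptive label covers the Section 6 endpoints as well as ABI, WIQ and TLR. Make the knee split exclusive, for example any below-knee treatment versus above-knee treatment only. Interaction tests do not control multiplicity by themselves (about 20% for four of them), so the exploratory label is needed too.

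If the sponsor wants a formal claim on a particular secondary endpoint, a fixed testing order after the primary is the alternative.

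The change affects wording only; no sample size or data collection changes. The sponsor gives up nominal significance claims on secondary endpoints and subgroups. Interaction tests also have low power at this size (about 31% for a 15-point difference between two equal strata), so a non-significant interaction must not be read as proof of a uniform effect.

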#### **20. Post-procedure endpoints**

Post-procedure information will be collected at regularly scheduled follow-up examinations, as detailed in the clinical trial schedule, and will be summarized using the descriptive statistics described above.

## **Primary Endpoint**

For the primary endpoint of 12-month composite of primary patency, limb salvage, MI, ischemic stroke and survival, with 95% confidence bounds will be calculated in the active arm and compared to control treatment duration. If this bound is less than that of control, then the primary endpoint will be considered met. All enrolled subjects are to be assessed for adverse events at follow-up visits. Assuming a maximum of 10% attrition due to non-compliance, loss to follow-up or death or non-compliance with follow-up, a minimum of 184 subjects in each arm are expected to be evaluable for the primary endpoint.

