## 17. Analysis set

The primary endpoint will be analyzed on an intent-to-treat basis and on a per-protocol basis analysis will also be performed. For intent-to-treat analysis, all subjects who sign the IRB/ECapproved written Informed Consent form and are enrolled into the trial will be included in the analysis, regardless of whether they receive the control or active arm drug treatments for the assigned durations or not. For per-protocol analysis, only subjects who receive the control or active arm drug treatments for the assigned durations will be included in the analysis.

The primary analysis set for testing of the primary endpoint is the intent-to-treat analysis set. No formal interim analyses are planned for the purpose of stopping this trial early for efficacy.

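### The only stated success rule for the primary endpoint compares an unnamed active-arm 95% bound with an unnamed control quantity, and conflicts with the two-sided 0.05 comparison in Sections 14 and 19

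*Combined protocol and SAP*

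**What the plan says.** Section 20 (Primary Endpoint) describes the outcome as a "12-month composite of primary patency, limb salvage, MI, ischemic stroke and survival". It then says that "95% confidence bounds will be calculated in the active arm and compared to control treatment duration", and gives the decision rule: "If this bound is less than that of control, then the primary endpoint will be considered met". The same paragraph expects at least 184 evaluable subjects per arm after "10% attrition due to non-compliance, loss to follow-up or death".

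Other sections point to an ordinary between-arm test:

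- Section 14 plans to detect a fall from 49% to 34% "with 80% power at the two-sided, 0.05 significance level".
- Section 17: "The primary analysis set for testing of the primary endpoint is the intent-to-treat analysis set".
- Section 19: "Discrete variables will be presented as frequencies and group percentages and compared using the chi-square test", and "For all comparisons a two-sided probability of <0.05 will be considered statistically significant". It does not tie the chi-square test to the primary endpoint by name.
- Section 16 foresees models for censored data where outcomes are times to event, and Section 20 (Other Analysis Methods) foresees Kaplan-Meier plots. Neither names a primary test.

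The horizon also differs. The Section 20 paragraph works at 12 months, whereas the Synopsis and Sections 6 and 14 use 12 months or the end of study treatment, whichever comes later. Under Section 9, treatment lasts 12 months longer in the active arm.

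**The concern.** A rule that declares success must fix three things: the statistic, the value it is compared with, and the error rate that follows. This rule fixes none of them. The text moves from bounds in the plural to a single bound without saying upper or lower. The control side could be the control arm's own bound or its observed rate. No difference, ratio or hazard ratio is estimated.

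An analyst could follow Section 20 because it is specific to the primary endpoint, or Section 19 because it covers all comparisons. The same data can then be reported as a success or a failure, and the choice could be made after the results are known.

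Replacing the rule with a two-arm test raises a linked question, the length of follow-up over which the arms are compared, because the plan gives two horizons and one of them can differ by arm.

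**Working it through.** **Inputs.** Event rates 49% and 34%, two-sided 0.05, 80% power, 10% dropout, 404 randomized (Section 14); 184 evaluable per arm (Section 20). Assumed: two-sided 95% Wald bounds, a binary outcome on the failure scale of Section 6, no censoring.

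**The plan's own sample size.** The two-proportion formula is

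n = [1.96·√(2p̄(1−p̄)) + 0.842·√(p₁(1−p₁)+p₂(1−p₂))]² / (p₁−p₂)²

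With p₁ = 0.49, p₂ = 0.34 and p̄ = 0.415 it gives 168.2, so 169 per arm. The continuity-corrected form, (n/4)·[1+√(1+4/(n·0.15))]², gives 181.3, so 182 per arm and 364/0.9 = 404.4 in total. That is close to the stated 404; without the correction the total is 338/0.9 = 375.6. The plan names no formula, but N fits a two-sided comparison of two proportions, so the problem lies in the decision rule and not in how N was obtained.

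**Three readings of the rule.** At 49%, one arm's standard error is √(0.49×0.51/184) = 0.0369, and that of the difference is √2×0.0369 = 0.0521.

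1. Active bound below the same bound in control. With equal arms this asks only which observed rate is lower. With no effect that happens in just under half of trials (ties excluded).
2. Active upper bound below the control estimate. This needs a difference above about 1.96×0.0369 = 0.072, or 0.072/0.0521 = 1.39 standard errors.
3. Active upper bound below the control lower bound. This needs about 2×0.072 = 0.144, or 2.77 standard errors.

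The uncorrected chi-square test needs 1.96×0.0521 = 0.102.

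Exact enumeration of all 185×185 outcome pairs gives the probability of success:

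| Rule | 49% vs 49% | 49% vs 34% |
|---|---|---|
| 1. Same bound in each arm | 47.9% | 99.8% |
| 2. Active upper vs control estimate | 8.0% | 94.3% |
| 3. Active upper vs control lower | 0.28% | 57.3% |
| Chi-square, favouring active | 2.7% | 83.5% |

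Wilson bounds change little: 47.9%, 8.0% and 0.28%, then 99.8%, 93.4% and 55.7%.

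**Example.** Control 90/184 is 48.9% (41.7% to 56.1%). Active 75/184 has an upper bound of 47.9%: met on readings 1 and 2, although p = 0.116. Active 68/184 has an upper bound of 43.9%: not met on reading 3, although p = 0.021.

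**Horizon.** Let D be the clinically indicated duration in months, 12 or less; values of 1, 3 and 6 are assumed. Under the whichever-is-longer wording a control subject is counted to month 12 and an active subject to month 12+D. With a constant hazard and no drug effect, the expected crude active-arm proportion is 1−0.51^((12+D)/12), that is 51.8%, 56.9% or 63.6%, against 49% in control.

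A common 12-month horizon removes that imbalance but has its own price. Both arms receive the same dual therapy during D, so a treatment contrast can arise only afterwards. Take the hazard ratio matching 49% versus 34%, ln(0.66)/ln(0.51) = 0.617, and let it act only after D. The 12-month active risk is 1−0.51^([D+0.617(12−D)]/12):

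| D (months) | Active risk | Chi-square power, 184 per arm |
|---|---|---|
| 1 | 35.4% | 75.7% |
| 3 | 38.1% | 56.5% |
| 6 | 42.0% | 27.9% |

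**The case against.** The strongest reply is that Section 20 contains one stray sentence. The Synopsis statistics section has no bound rule, Section 14 sizes for a two-sided 0.05 test, Section 17 speaks of testing in the intention-to-treat set, and Section 19 covers every comparison. If Section 19 was always meant to govern, the error rate is sound. That stands, and it limits the claim. A reader might infer that this trial has a false-positive rate near 48%. The documents do not support that: the figure belongs to one reading of an ambiguous sentence. What remains is that the only text defining success says something else and is not reconciled with the rest.

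The direction of the composite and the status of death might also seem open. They are not: Section 6 defines the composite as failures and counts death from any cause as an event. Only the Section 20 wording is out of line.

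A reader might further conclude that unequal follow-up must bias the result, or that missing data are left wholly unaddressed. Neither follows. The bias arises for a crude proportion under the whichever-is-longer wording. Section 16 provides for censored-data models where appropriate, a comparison of subjects with and without data, and a check on the robustness of the primary conclusion.

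**Conclusion.** The concern holds and should be fixed before analysis. The rule that decides whether the trial is positive is undefined and conflicts with the two-sided 0.05 comparison elsewhere in the plan. None of the three readings examined has the operating characteristics of the stated design: readings 1 and 2 are too lenient, and reading 3 is too strict and loses power. The percentages rest on 184 per arm, Wald bounds and a binary endpoint, and show how far the readings diverge; they do not estimate the trial's actual error rate.

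It would be tempting to add that a 12-month horizon settles everything at the present sample size. The documents do not support that. Section 5 concerns an extension that begins after the indicated duration, and 12 months from the index procedure cuts off part of it. If the effect starts only then, power falls below the planned 80%, to about 76%, 56% or 28% for assumed durations of 1, 3 or 6 months with a constant hazard and a hazard ratio of 0.617.

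**What to change.** 1. Delete the bound rule in Section 20. State that the primary endpoint is met if the between-arm comparison of the Section 6 failure composite, in the intention-to-treat set, is significant at two-sided 0.05 in favour of the active arm. Use the Section 19 chi-square test, or a log-rank or Kaplan-Meier comparison, which would fit Section 16 and the Kaplan-Meier plots in Section 20. Report the between-arm difference with its 95% confidence interval.
2. In the same edit, reconcile the horizon across the Synopsis and Sections 6, 14 and 20 so that both arms are compared over the same length of follow-up. A censored-data analysis over a common horizon avoids the imbalance of a crude proportion.
3. Remove death from the list of attrition reasons in Section 20, since Section 6 counts it as an event.

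Items 1 and 3 cost only wording. Item 2 is a choice for the sponsor: 12 months from the index procedure needs no new data but truncates the extension and may lose the power shown above, while a longer common horizon needs longer follow-up of the control arm. Power should be rechecked for whichever horizon is chosen.
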